4. SELECTION AND ENROLLMENT OF PARTICIPANTS

4.1 Inclusion Criteria

Participants must meet all of the inclusion criteria to participate in this study:

1. History of T2DM mellitus. If taking insulin, screening labs will include C-Peptide to rule out T1DM. The study intervention is not designed for people with Type 1 diabetes who make no insulin.
2. HbA1c > 6.5% and < 12.0% at screening. The lower limit confirms the diabetes diagnosis. Persons with a HbA1c > than 12% typically need immediate attention to the medical regimen, and we aim to have this done before entering the trial to better separate the effects of improved medical regimens from the diet intervention. Potential participants with a HbA1c > 12% can be enrolled once glucose control is improved.
3. Experience food-related cravings most days of the week and eat in response to these cravings regularly. A key hypothesis is that our mindfulness approach will reduce cravings and craving-related eating, and this is primary mechanistic outcome. Thus we need to recruit participants who experience this.
4. Aged 18 years old and older. We are not enrolling younger children as they may need an intervention that is better tailored to children.
5. Able to engage in light physical activity. We will be recommending physical activity as part of the intervention.
6. Willing and able to participate in the interventions. Must be interested in following a carbohydrate- restricted diet, willing to learn about mindful eating and behavioral strategies for following prescribed diets, have sufficient control over their food intake so that they can follow either diet, and otherwise be able and willing to participate in the intervention. Intervention content must be practiced to evaluate whether it is effective.
7. Have smartphone and are willing to use it on a regular basis for data collection (e.g. craving EMA assessment).
8. Ability to speak English. Groups will be conducted in English, and we do not have the capacity, given the resources available in this proposal, to translate all course material and conduct groups into another language. We enrolled Hispanic participants into the pilot study who were fluent in English, and expect to do this in the proposed study.

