2. Hypoglycemia: The carbohydrate restricted diet may lead to decreases in glucose levels. In persons receiving medications such as sulfonylureas or insulin, this could increase the risk of hypoglycemia if appropriate medication adjustments are not made while the participant is transitioning into nutritional ketosis (once in nutritional ketosis, beta-hydroxybutyrate as a preferred CNS fuel offers some protection against symptomatic hypoglycemia.⁵⁶). In our pilot study, we used a medication reduction algorithm that resulted in no episodes of hypoglycemia. For the proposed study, we will use a similar algorithm.

Initial HbA1c	Initial medication reduction
6.5-7.0%	
 • Continue: Metformin, TZD • Reduce by 50%: Basal insulin • Stop: Secretagogue, prandial insulin, pre-mixed insulin, acarbose, GLP-1 ag/DPP4 inhibitor
7.1-8.0%	
 • Continue: Metformin, TZD • Reduce by 50%: Basal insulin, pre-mixed insulin, secretagogue, GLP-1 ag/DPP4 inhibitor • Stop: Acarbose, prandial insulin
8.1-12%	
 • Continue Metformin, TZD, secretagogue, basal insulin, GLP-1 ag/DPP4 inhibitor • Reduce by 50%: Pre-mixed insulin, • Stop: Acarbose, prandial insulin

TZD: thiazolidinedione; secretagogue: sulfonylureas and meglitinides; GLP-1 ag: glucagon like peptide 1 agonist; DPP-4 inhibitor: dipeptidyl peptidase 4

For the first 6 weeks of the trial, participants on non-insulin medications will be asked to check blood glucose (BG) fasting and pre-dinner. If taking insulin, participants will be asked to check BG before each injection (standard of care). BGs will be reviewed on a weekly basis by study physicians, including an endocrinologist. If the majority of BG values drop below 110, or there are other concerning BG patterns, we will reduce/stop medications in the following order:

1. Pre-mixed insulin
2. Secretagogue
3. GLP-1 ag/DPP4 inhibitor
4. Basal Insulin

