7.4 Reporting Procedures

Serious Adverse Event reporting will be in accordance with the UCSF IRB Regulations (<http://irb.ucsf.edu/sites/hrpp.ucsf.edu/files/post-approval-reporting-summary-sheet.pdf>) and Code of Federal Regulation Title 21 Volume 5 Part 312.32.

Incidents or events that meet the OHRP criteria for unanticipated problems require the creation and completion of an unanticipated problem report form. OHRP recommends that investigators include the following information when reporting an adverse event, or any other incident, experience, or outcome as an unanticipated problem to the IRB:

- Appropriate identifying information for the research protocol, such as the title, investigator's name, and the IRB project number;
- A detailed description of the adverse event, incident, experience, or outcome;
- An explanation of the basis for determining that the adverse event, incident, experience, or outcome represents an unanticipated problem;
- A description of any changes to the protocol or other corrective actions that have been taken or are proposed in response to the unanticipated problem.

Adverse Event Reporting

SAEs that are unanticipated, serious, and possibly related to the study intervention will be reported to the Independent Safety Monitor(s), UCSF IRB, and NCCIH in accordance with requirements.

- Unexpected fatal or life-threatening AEs related to the intervention will be reported to the NCCIH Program Officer, and Independent Safety Monitor(s) within 3 days of the investigator becoming aware of the event. Other serious and unexpected AEs related to the intervention will be reported within 5 working days.
- Anticipated or unrelated SAEs will be handled in a less urgent manner but will be reported to the Independent Safety Monitor(s), IRB, and other oversight organizations in accordance with their requirements and will be reported to NCCIH on an annual basis.
- All other AEs documented during the course of the trial will be reported to NCCIH on an annual basis by way of inclusion in the annual report and in the annual AE summary which will be provided to NCCIH and to the Independent Monitors. The Independent Safety Monitor(s) Report will state that all AEs have been reviewed.

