7.6 Safety Monitoring

While the overall risks of this study are low, due to clinical trial design and the use of a treatment that has a low but possible risk of serious adverse effects, we will employ a two-person data safety-monitoring board with outside reviewers. The outside reviewers will not otherwise be part of the study team, and will include an experienced clinical investigators and statistician. The reviewer's CVs will be submitted to NIH, and agreement will be obtained from NIH that the reviewers are suitably qualified before beginning the study. The PI will ensure continuous and close monitoring of participant safety. The PI will report to the DSMB. Study progress and safety will be reviewed weekly by the PI and core study team. A report that will be submitted to the outside reviewer will be compiled every 6 months and will include a list and summarization of adverse events. In addition, the report will address (1) whether adverse event rates are consistent with pre-study assumptions; (2) reason for dropouts from the study; (3) whether all participants met entry criteria; and (4) whether continuation of the study is justified on the basis that additional data are needed to accomplish the stated aims of the study. If the DSMB requires an interim analysis based on the occurrence of severe adverse events, we will develop plans for conducting these in consultation with the statistician on this RCT. The outside monitoring reports will be increased in frequency if two or more Serious Adverse Event's (SAE's) with attribution to study related procedures as possibly, probably or definitely related occur in a six-month period of time. In this situation, SAE's will be reported monthly, and study procedures will be reviewed to determine if changes are needed to reduce the risk of SAEs.

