9.5.2 Secondary Outcomes

Secondary mechanistic outcomes: We have four additional mechanistic measures to assess our hypothesis that mindfulness training will enhance dietary adherence:

- Enhanced ability to reduce craving-related eating/decreased impulsivity as measured by the Delayed Discounting or Relative Reinforcing Value of Food task.
- Decreased stress-related eating as measured by the Palatable Eating Motives Scale (PEMS) subscale for stress-related eating as a coping mechanism.
- Decreased emotion related eating as measured by the Emotional Overeating Questionnaire.
- Improved resilience (resumption of dietary adherence) after dietary non-adherence occurs. Our key measure will be the time from a ketone measure of < 0.2 mmol/L to higher levels of > 0.2 mmol/L, indicating a return to nutritional ketosis after a period of consuming foods that depress ketosis.

Secondary clinical outcomes:

- Glycemic control, using HbA1c. We view improving HbA1c as the primary clinical outcome that we seek to improve in subsequent studies.
- Fasting glucose
- Homeostatic model assessment (HOMA) index of insulin resistance (computed from insulin and fasting glucose measures)
- Weight
- Adherence to diet measured by 24-hour diet recall and by ketone measures

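### In the protocol text shown, insulin is reduced on a ketosis-inducing diet, but no upper ketone value sends a home reading to a physician

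*Combined protocol and SAP*

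**What the plan says.** Section 2.2 sets carbohydrate at about 10% of calories, chosen partly because this induces a low level of ketosis that can serve as an adherence biomarker. The same section contains the only mention of diabetic ketoacidosis in the text shown, to say that nutritional ketosis differs from it.

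Insulin users are eligible. Section 4.1 adds a check for them: "If taking insulin, screening labs will include C-Peptide to rule out T1DM".

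Section 7.1 cuts glucose-lowering drugs at the start of the diet according to HbA1c. In the highest band (8.1-12%) the entry for drugs left unchanged reads "Continue Metformin, TZD, secretagogue, basal insulin, GLP-1 ag/DPP4 inhibitor"; prandial insulin is stopped there, as in the other two bands. For follow-up, the section says "BGs will be reviewed on a weekly basis by study physicians, including an endocrinologist", and the trigger for further change is "If the majority of BG values drop below 110, or there are other concerning BG patterns, we will reduce/stop medications", followed by an ordered list in which basal insulin comes fourth.

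Section 6.2.4 gives every participant a meter that measures blood beta-hydroxybutyrate. Readings are requested three times a week for about 4 weeks and twice a week after that, and are reported through the EMA system. The schedule in section 6.1 labels ketone monitoring as a dietary adherence measure and home glucose monitoring as a safety measure. Section 6.2.4 gives the meter checks and downloads one purpose, which is to confirm the accuracy of reported values.

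**The concern.** The study lowers insulin while asking participants to follow a diet intended to raise ketones, and it already receives a blood ketone value from each of them several times a week. Yet the safety section is built around glucose that is too low. Its one numeric trigger is a low-glucose trigger, and its ordered steps all remove medication. A ketone value that is too high has no stated meaning and no stated recipient with clinical responsibility.

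Followed as written, a high reading in a participant whose insulin has been cut could sit in the EMA data without prompting clinical action. Ketoacidosis requiring admission would be recorded, but only afterwards, as a hospitalization. The stake is participant safety. Both arms follow the same diet and medication rules, and nothing here suggests bias between arms or a fault in the adherence endpoint.

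**Working it through.** No figure in the plan is in dispute, so the check is a count of what the text provides, followed by a workload estimate for the remedy.

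**Initial insulin changes (section 7.1 table)**

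| HbA1c band | Prandial | Pre-mixed | Basal |
|---|---|---|---|
| 6.5-7.0% | stop | stop | halve |
| 7.1-8.0% | stop | halve | halve |
| 8.1-12% | stop | halve | continue |

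Prandial insulin is stopped in 3 of 3 bands. Pre-mixed insulin is stopped in 1 and halved in 2. Basal insulin is halved in 2 and continued in full in 1. A participant who takes basal insulin therefore starts with at least half the dose in every band.

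**Ketone cut-offs stated**

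- Resilience outcome (sections 1.2, 9.1 and 9.5.2): "the time from a ketone measure of < 0.2 mmol/L to higher levels of > 0.2 mmol/L".
- Adherence (section 9.6): share of readings at or above 0.3 mmol/L.
- Upper values: none.

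That is two cut-offs, both at the low end and both for outcomes.

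**Who looks at what**

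- Study physicians, weekly: glucose, medication adjustments and reported symptoms (7.1). Ketones are not named.
- Staff, at class sessions and visits: meter data, for accuracy (6.2.4).
- Weekly EMA data review (10.3.3): odd responses are clarified with participants. Ketone values arrive through the EMA system, so this review may cover them, but it is a data-quality step with no ketone limit and no physician named.
- Listed diet risks (7.1): hyperlipidemia, hypoglycemia, kidney stones, bone turnover and minor effects.
- Solicited events (7.3): hospitalizations and hypoglycemic episodes.

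Ketoacidosis is in neither of the last two lists.

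**Workload of reviewing ketones, one R61 wave of 20, full compliance**

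- First 4 weeks or so: 20 × 3 = 60 readings a week.
- After that: 20 × 2 = 40 readings a week.
- The documents do not say how many participants use insulin. Assuming 10% to 50%, that is 20 × 0.10 = 2 to 20 × 0.50 = 10 people. They would supply 2 × 3 = 6 to 10 × 3 = 30 readings a week at first, then 2 × 2 = 4 to 10 × 2 = 20.

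These counts measure effort, not risk. The documents give no frequency of high readings and no ketoacidosis rate, so harm cannot be sized.

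**The case against.** The case for leaving the plan alone has real content.

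- **Screening.** C-peptide is measured in insulin users, people above HbA1c 12% wait until control improves, and renal and liver failure are exclusions.
- **Contact.** Physicians see glucose and symptoms weekly. Participants are told to report discomfort such as weakness or dizziness and are taught about diet side effects in class. Staff can page a physician, and primary care physicians are kept informed. Insulin users check glucose before each injection, with no end date given. Section 7.6 adds: "Study progress and safety will be reviewed weekly by the PI and core study team".
- **Ketone data are not ignored.** Meters are checked periodically in class, and the weekly EMA review may pick up odd values. With the pager, an informal route to a physician exists.
- **Experience.** Section 7.1 reports no serious adverse events in pilot testing.
- **Reporting.** Left unlisted, a related ketoacidosis SAE would ordinarily count as unexpected and go out within 3 days or 5 working days under section 7.4. Listing it could weaken that.

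Most of this stands, and it rules out several stronger readings. A reader might infer that insulin users are left without insulin; the table keeps at least half the basal dose initially for those who take it. A reader might infer that nobody looks at the ketone values; the class checks and EMA review say otherwise. A reader might infer that physicians can only take medication away. That is true of the ordered list, but section 7.1 goes on to let physicians suggest medication changes and consult primary care without limiting the direction.

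What the objection does not supply is an upper ketone value or a step that sends a ketone reading to a physician. The pager works only if someone recognizes a problem, and no ketone value is defined as one. The pilot result carries limited weight, because section 7.1 itself says long-term adverse events with these diets in type 2 diabetes have had little careful study. That section also lists kidney stones and bone effects on theoretical grounds, so the absence of observed cases is not the protocol's own test for naming a risk.

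**Conclusion.** The gap is real and narrow. In the protocol text shown, home ketones are collected while insulin is reduced, and no upper value or written step brings a high reading to a physician. Existing safeguards lower the chance that an episode goes unnoticed, but none is written to act on the ketone value.

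The size of the risk cannot be estimated. The documents do not support a claim that ketoacidosis is likely in this screened population, nor a claim that participants are uninformed: the consent form and class materials are not shown and may say what to do about a high reading. Readings two to three times a week may miss an episode, so the benefit is an added check and not assured early detection.

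This is a worthwhile low-cost improvement, held with medium confidence. It rests on the protocol text alone and on reading the EMA review as a data-quality step.

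**What to change.** In sections 7.1 and 7.2, add home ketone readings to the existing weekly physician review for as long as they are collected. Before enrolment, have the study endocrinologist set an upper value; none is proposed here, because the documents give no basis for one. State that a reported or downloaded reading above it leads to prompt physician contact by the existing pager route, with a check of glucose, symptoms and insulin dose. Say explicitly that insulin may be restored; this clarifies a power the text does not exclude.

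Naming ketoacidosis in 7.1 and 7.3 is optional and would by itself only be documentation. If it is done, section 7.4 needs a matching sentence, because that section says "Anticipated or unrelated SAEs will be handled in a less urgent manner": related ketoacidosis SAEs should stay on expedited reporting. Leave the adherence definition in section 9.6 as it is.

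The cost is protocol wording, one flag on data already received, and some physician time: up to about 60 readings a week to scan per wave of 20, more if waves overlap, with some harmless readings followed up.

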5. TZD
6. Metformin

Study physicians will review these medication adjustments as well as any symptoms reported by participants using information collected from participants on a weekly basis, and will communicate

suggested changes in diabetes medications to participants. Study participants will be able to contact study staff using a study phone number for questions or problems, and staff will be able to reach study physicians by pager for more urgent problems. As in our pilot study, primary care physicians for participant will receive information about the study before the participant begins the study. Study physicians will help to make sure that primary care physicians informed of any suggested changes to medication regimens, and will consult with primary care physicians where indicated.

3. *Other theoretical risks* of the carbohydrate restricted diet include nephrolithiasis and increased bone turnover. The potential for these side effects is derived from pathophysiologic theory, studies of the diet using intermediate endpoints, and extrapolation from similar diet approaches, such as the ketogenic diet for epilepsy. Because kidney stones and bone fractures have not been reported as an actual adverse effect of this diet in the research literature, we cannot estimate their frequency. We will be recording adverse events that occur during the study.

4. *Minor adverse effects*: With this diet, several minor side effects may occur and include constipation, headache, muscle cramps, diarrhea, general weakness, and rash. Most of these occur at diet initiation, are short-lived, and are generally alleviated by adequate fluid intake and other minor diet modifications that will be thoroughly addressed in the intervention. Participants will be instructed to speak to the instructor *or contact study staff* if they experience discomfort, such as constipation, diarrhea, weakness, muscle cramps, or dizziness. There is extensive instruction during class on how to address any potential side effects stemming from the diet.

7.2 Methods and Timing for Assessing, Recording, and Analyzing Safety Parameters

Unanticipated problems will be recorded in the Salesforce study database throughout the study. We will record all reportable events with start dates occurring any time after informed consent is obtained until 7 (for non-serious AEs) or 30 days (for SAEs) after the last day of study participation. At each study visit, the investigator will inquire about the occurrence of AE/SAEs since the last visit. We will monitor serum fasting lipid profiles at baseline, 3, and 6 months (also 12 mos in R33 phase). Events will be followed for outcome information until resolution or stabilization.

Safety parameters will be reviewed and analyzed per the schedule below.

Data type	Frequency of review	Reviewer
AEs and rates (including out-of-range lab values)	Monthly	PI, Internal QA Reviewer
	Semi-annually	Independent Monitors
	Annually	NCCIH
SAEs (unexpected and related)	Per occurrence	PI, Independent Monitors, NIH/NCCIH
SAEs (expected or unrelated)	Per Occurrence	PI, Internal QA Reviewer
	Annually	Independent Monitors, NIH/NCCIH
Unanticipated Problems	Monthly	PI, Internal QA Reviewer
	Per Policy	IRB

Study progress and safety will be reviewed monthly (and more frequently if needed). Progress reports, including patient recruitment, retention/attrition, and AEs will be provided to the Monitoring Committee semi-annually. An Annual Report will be compiled and will include a list and summary of AEs. In

addition, the Annual Report will address (1) whether AE rates are consistent with pre-study assumptions; (2) reason for dropouts from the study; (3) whether all participants met entry criteria; (4) whether continuation of the study is justified on the basis that additional data are needed to accomplish the stated aims of the study; and (5) conditions whereby the study might be terminated prematurely. The Annual Report will be sent to the Independent Monitor and will be forwarded to the IRB and NCCIH. The IRB and other applicable recipients will review progress of this study on an annual basis

7.3 Adverse Events and Serious Adverse Events

An **adverse event (AE)** is generally defined as any unfavorable and unintended diagnosis, symptom, sign (including an abnormal laboratory finding), syndrome or disease which either occurs during the study, having been absent at baseline, or if present at baseline, appears to worsen. Adverse events are to be recorded regardless of their relationship to the study intervention.

A **serious adverse event (SAE)** is generally defined as any untoward medical occurrence that results in death, is life threatening, requires inpatient hospitalization or prolongation of existing hospitalization, results in persistent or significant disability/incapacity, or is a congenital anomaly.

Laboratory values that will be collected to assess safety: We will monitor serum fasting lipid profiles at baseline, 3, and 6 months (also 12 months in R33 phase). Abnormal lipid values are defined using the Common Terminology Criteria for Adverse Events (CTCAE) v 4.0 criteria provided below (https://evs.nci.nih.gov/ftp1/CTCAE/Archive/CTCAE_4.02_2009-09-15_QuickReference_5x7_Locked.pdf).

Adverse Event: Hypertriglyceridemia

Short Name: Hypertriglyceridemia

MedDRA Code: 10020870

Grade	Description
1	150 mg/dL - 300 mg/dL; 1.71 mmol/L - 3.42mmol/L
2	>300 mg/dL - 500 mg/dL; >3.42 mmol/L- 5.7 mmol/L
3	>500 mg/dL - 1000 mg/dL; >5.7 mmol/L - 11.4 mmol/L
4	>1000 mg/dL; >11.4 mmol/L; life-threatening consequences
5	Death

Adverse Event: Cholesterol high

Short Name: Cholesterol high

MedDRA Code: 10008661

Grade	Description
1	>ULN - 300 mg/dL; >ULN - 7.75 mmol/L
2	>300 - 400 mg/dL; >7.75 - 10.34 mmol/L
3	>400 - 500 mg/dL; >10.34 - 12.92 mmol/L
4	>500 mg/dL; >12.92 mmol/L

AEs to be collected as solicited events at study visits include recent hospitalizations and hypoglycemic episodes. Unsolicited events will be recorded in the study Salesforce database. AE data that is formally assessed at study visits will be compared to existing unsolicited events in participant records to avoid double capture.

